7.2. Screening and Critical Baseline Assessments

Written informed consent must be obtained from each potentially eligible participant by study site personnel prior to the initiation of any Screening procedures as outlined in this protocol. The consent form must have been approved by the Institutional Review Board (IRB)/Independent Ethics Committee (IEC). After signing an informed consent, participants will complete Screening assessments to determine participant eligibility. Each participant being screened for study enrollment evaluation will be assigned a participant number at the Screening visit. This number will be given sequentially in chronological order of participant presentation according to a numeric roster provided by GSK.

7.2.1. Screening Assessments

Eligibility criteria must be carefully assessed at the Screening visit. Physical examinations should be conducted as part of normal routine clinical care. Background information to be collected at Screening includes demography and prior ART history.

Eligible participants may be randomly assigned immediately as soon as all Screening assessments are complete and the results are available and documented. All participants will complete the screening period of approximately 14 days prior to Baseline (Day 1) during which all clinical and laboratory assessments of eligibility must be performed and reviewed. The Screening period may be extended to 35 days to accommodate availability of all Screening assessment results, completion of source document verification to satisfy the Inclusion and Exclusion Criteria, and scheduling. All Screening results **must** be available prior to randomization.

All information about the participant's current regimen must be available for review by the Principal Investigator or designee prior to randomization. Source documents from other medical facilities must be located/received during the 14 day (up to 35 days) screening period and under no circumstances may the participant be randomized in the absence of source documentation even if there are delays in receipt of this information.

Any available prior genotypic resistance testing must be provided to GSK, after screening and before randomization according to guidance in the SPM, to provide direct evidence of no pre-existing exclusionary resistance mutations. The lack of exclusionary resistance mutations must be confirmed by the study virologist, which will be provided before the screening window closes. Details on use of RAMOS for tracking historic resistance report availability and submission to ViiV Healthcare Virology for evaluation are described in the SPM. Details regarding baseline or prior resistance data must be noted in the source documentation.

Participants infected with HBV will not be enrolled in the study. Evidence of HBV infection is based on the results of testing at Screening for hepatitis B surface antigen (HBsAg), hepatitis B core antibody (anti-HBc), hepatitis B surface antibody (anti-HBs), and HBV DNA. HBV DNA will only be performed for participants with positive anti-HBc and negative HBsAg and negative anti-HBs (past and/or current evidence).

Participants with an anticipated need for HCV therapy during the study must not be enrolled into this study, as HCV therapy currently includes the prohibited medication interferon. The length of this study should be considered when assessing the potential need for therapy.

All participants will be screened for syphilis. Participants with untreated syphilis infection, defined as a positive RPR without clear documentation of treatment, are excluded. Participants with a serofast RPR result despite history of adequate therapy and no evidence of re-exposure may enrol after consultation with the Medical Monitor. Participants with a positive RPR test who have not been treated may be rescreened at least 30 days after completion of antibiotic treatment for syphilis.

The eCSSRS (see Section 7.4.6) assessed at the Screening visit will assess the participant's lifetime risk (any suicidal ideation, behavior, etc. occurring over the participant's lifetime). A positive alert (indicating some risk) is not necessarily exclusionary, rather a means to assess overall risk.

Participants who meet all entry criteria are randomized and assigned a randomization number. A single repeat of a procedure/lab parameter is allowed to determine eligibility (unless otherwise specified). Participants not meeting all inclusion and exclusion criteria at initial screen may be rescreened and receive a new participant number one time unless they were excluded for reason of having exclusionary historic genotypic resistance. Participants who are randomized into the trial and subsequently withdrawn from the study for any reason may not be rescreened.

7.2.2. Baseline Assessments

At Day 1 and prior to randomization, any changes to the eligibility parameters must be assessed and any results required prior to randomization (e.g., Day 1 urine pregnancy test for women of childbearing potential) must be available and reviewed. The following demographic parameters will be captured: year of birth, sex, race and ethnicity. Medical/medication/family history will be assessed as related to the inclusion/exclusion criteria listed in Section 5.

HIV-1 genotypic resistance testing and plasma HIV-1 RNA measurement results from Screening must be available prior to the Baseline visit.

Baseline information to be collected at Day 1 includes general medical history and current medical conditions. Laboratory and health outcomes assessments will also be assessed. Questionnaire/surveys are recommended to be administered at the beginning of the visit before any other assessments are conducted, in the order specified. For participants who agree to the optional assessment, a whole blood sample for genetic research should be collected at Day 1 (if not already collected during participation in the ATLAS study).

In addition to a full routine medical history at Baseline, more detailed information will be collected for some disease processes such as:

- Cardiovascular medical history/risk factors (as detailed in the eCRF) will be assessed at Baseline and assessments will include height, weight, blood pressure, smoking status and history, pertinent medical conditions (e.g., hypertension, diabetes mellitus), and family history of premature cardiovascular disease. In addition, medical history/risk factors for renal disease such as nephropathy, renal failure, and nephrolithiasis will be assessed.
- history of illicit drug use [e.g., cocaine, heroin, and methamphetamine use];
- intravenous drug use history;
- gastrointestinal disease (e.g., GI bleeding, PUD, etc.);
- metabolic (e.g., Type I or II diabetes mellitus);
- psychiatric (e.g., depression);
- renal (e.g., nephrolithiasis, nephropathy, renal failure); and,
- neurologic disorders

Procedures conducted as part of the participant's routine clinical management [e.g., laboratory assessments] and obtained prior to signing of informed consent may be utilized for Screening or baseline purposes provided the procedure meets the protocol-defined criteria and has been performed in the timeframe of the study. Where possible local lab results should be confirmed by submission of samples to the central lab.

7.3. Efficacy

7.3.1. Plasma HIV-1 RNA

Plasma for quantitative HIV-1 RNA will be collected according to the Time and Events schedule (Section 7.1). Methods to be used may include but are not limited to the Abbott RealTime HIV-1 Assay lower limit of detection (LLOD) 40 c/mL. In some cases, (e.g., where the HIV-1 RNA is below the lower limit of detection for a given assay) additional exploratory methods will be used to further characterize HIV-1 RNA levels.

7.3.2. Lymphocyte Subsets, CD4+ and CD8+

Lymphocyte subsets will be collected for assessment by flow cytometry (total lymphocyte counts, percentage and absolute CD4+ and CD8+ lymphocyte counts, ratios) according to Time and Events schedule (Section 7.1) and Laboratory Assessments (Section 7.4.2).

7.3.3. HIV Associated Conditions

HIV-associated conditions will be recorded as per Time and Events schedule (Section 7.1). HIV-associated conditions will be assessed according to the 2014 CDC Revised Classification System for HIV Infection (see Section 11.4).

7.4. Safety

7.4.1. Clinical Evaluations

The following clinical evaluations will be performed according to the Time and Events schedule:

- Monitoring and recording of all AEs and SAEs. Additional information on the Time Period and Frequency of Detecting AEs and SAEs is provided in Section [7.4.3.1](#).
- Physical exams should be conducted as part of normal routine clinical care. Abnormalities noted during any exam must be recorded in the eCRF (e.g., in the current medical conditions or AE logs).
- Height and weight will be measured and recorded. Height collected on the Day 1 (Baseline) only.
- Vital signs will include systolic and diastolic blood pressure and heart rate collected after resting for about 5 minutes. Temperature will also be collected.
- Past medical history, family history, social history, medication history. Targeted history on cardiovascular risk (smoking history, family and personal history).
- HIV-associated conditions will be recorded.
- Electrocardiogram: A 12-lead ECG will be performed in a semi-supine position after 5 minutes of rest. On Day 1 (Baseline) of the Maintenance Phase, ECGs should be performed in triplicate prior to first dose. An ECG machine that automatically calculates the heart rate and measures PR, QRS, QT, and QTc intervals is preferred, and these calculated numbers can be used for reporting purposes. Otherwise, an appropriately qualified ECG reader must interpret the results. The same interpreter should assess all ECGs for each participant for the site. Regardless, each ECG should be reviewed by a qualified ECG reader. The qualified ECG reader will make the non-calculated ECG interpretations. The same QT correction formula must be used for each individual participant to determine eligibility for and discontinuation from the study. This formula may not be changed or substituted once the participant has been enrolled.
- Regular monitoring of hematology, blood chemistry, urinalysis and fasting glucose and lipids (parameters to be tested listed below).
- Periodic assessment of glucose, insulin, and bone, cardiovascular, and renal markers;
- Pregnancy testing. A negative urine pregnancy test is required prior to initiation of IP, any dose of CAB LA or RPV LA or as required by the Medical Monitor following a treatment interruption(s). If serum testing is required locally, the results should be available prior to the visit where urine testing is indicated per the Time and Events Schedule (Section [7.1](#)).
- Evaluation and documentation of all concomitant medications and blood products.

- Injection Site Reactions (ISRs) will be assessed clinically during the Maintenance and Extension Phases for the following:
Pain, tenderness, pruritis, warmth, bruising, discoloration, infections, rash, erythema, swelling, induration, and nodules (granulomas or cysts).
- A clinical assessment (using Division of Acquired Immunodeficiency Syndrome [DAIDS] grading scale) should be performed both before and after an injection to identify resolving and new ISRs. All injection site reactions are considered adverse events. The clinical assessment and interpretation of any ISR, will be documented in the ISR AE eCRF.
- Columbia Suicide Severity Rating Scale (eC-SSRS) will be assessed as per the Time and Events Schedule (see Section 7.1 and Suicidal Risk Monitoring Section 7.4.6).

Any appropriately qualified site personnel (e.g., Investigator, sub-Investigator, or study coordinator/nurse) can perform assessments.

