	
established at the mid dose 5 mg/kg/day, the maternal exposure at this dose calculated using systemic exposure from non-pregnant rats is >20 fold predicted Cmax and AUC exposures for anticipated clinical CAB LA exposures for HIV treatment
 
The clinical significance in humans of these findings is unknown.
	
throughout the long term follow up phase of this study following exposure to CAB LA.
 
 FRP are also required to undergo regular pregnancy testing throughout study conduct to enable early discontinuation of CAB LA once pregnancy is identified.

Development of Resistance following discontinuation of CAB LA
	
Residual concentrations of CAB would remain in the systemic circulation of participants who stop CAB LA treatment for prolonged periods (more than 1 year, in some subjects, GlaxoSmithKline Document Number 2016N269422_00) after last injection (e.g., for tolerability issues or treatment failure). Participants discontinuing CAB LA regimen may be at risk for developing HIV-1 resistance to CAB many weeks after discontinuing injectable therapy.
	
 After participants stop CAB LA, Oral HAART regimens will be prescribed within 4 weeks after the last Q4W dose or within 8 weeks after the last Q8W dose, and following consultation with the medical monitor. This would be anticipated to result in continued suppression or rapid resuppression of HIV-1 RNA thus minimizing the risk of emergent resistance The participants in this study who discontinue IM CAB for any reason will be monitored for a minimum of 52 weeks from the time of the last IM CAB injection.

Potential Risk of Clinical Significance	Summary of Data/Rationale for Risk	Mitigation Strategy

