The second and third IM injections with CAB LA 400 mg and RPV LA 600 mg will be performed at Week 8 and Week 12. There will be a -7-day dosing window for the second and third IM injections such that the second injection occurs within the window of Week 7 and Week 8 but no later than Week 8 and the third injection occurs within the window of Week 11 and Week 12 but no later than Week 12. Subsequent injections with CAB LA 400 mg and RPV LA 600 mg will occur every 4 weeks (± 7 days) thereafter. In addition, starting after the Week 16 injection, the interval between injection visits will be limited to a maximum of 5 weeks. The Medical Monitor must be contacted to discuss individual participant case management if the length of time between injections exceeds or is projected to exceed 5 weeks.

4.2.2.1.2. IM injections every 8 weeks (Q8W from SOC):

Week 4b visit – CAB LA 600 mg + RPV LA 900 mg IM, each given as 1 X 3 mL IM injection

Week 8 visit- CAB LA 600 mg + RPV LA 900 mg IM, each given as 1 X 3 mL IM injection

Week 16 visit and Q8W thereafter - CAB LA 600 mg + RPV LA 900 mg IM, every 8 weeks for 100 weeks, each given as 1 X 3 mL IM injection

At the Week 4b visit, subjects will return to the clinic, take their last oral dose (CAB 30 mg + RPV 25 mg), and receive the first CAB LA (600 mg) + RPV LA (900 mg) injections (within 2 hours of the final oral dose of CAB + RPV). The first injections with IM CAB LA + RPV LA at Week 4b can be performed once central lab results are available and safety parameters are reviewed from the Week 4a visit.

The second loading injection will be administered at Week 8 (CAB LA 600 mg + RPV LA 900 mg, with subsequent injections (CAB LA 600 mg + RPV LA 900 mg) occurring every 8 weeks thereafter. There will be a -7-day dosing window for the second and third IM injections such that the second injection occurs within the window of Week 7 and Week 8 but no later than Week 8 and third injection occurs within the window of Week

15 and Week 16 but no later than Week 16. Subsequent injections with CAB LA 600 mg and RPV LA 900 mg will occur every 8 weeks (± 7 days). Starting after the Week 16 injection, the interval between injection visits will be limited to a maximum of 9 weeks. If the length of time between injections exceeds, or is projected to exceed 9 weeks, the Medical Monitor must be contacted to discuss individual participant case management.

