Week 8 and Q8W thereafter- CAB LA 600 mg + RPV LA 900 mg IM, each given as 1 X 3 mL IM injection

The second loading injection will be administered at Week 8 (CAB LA 600 mg + RPV LA 900 mg), with subsequent injections (CAB LA 600 mg + RPV LA 900 mg) occurring every 8 weeks thereafter. There will be a -7-day dosing window for the second and third IM injections such that the second injection occurs within the window of Week 7 and Week 8 but no later than Week 8 and third injection occurs within the window of Week 15 and Week 16 but no later than Week 16. Subsequent injections with CAB LA 600 mg and RPV LA 900 mg will occur every 8 weeks (± 7 days). Starting after the Week 16 injections, the interval between injection visits will be limited to a maximum of 9 weeks. If the length of time between injections exceeds, or is projected to exceed 9 weeks, the Medical Monitor must be contacted to discuss individual participant case management.

The primary study analysis will consist of data collected through the Week 48 visit. A single repeat of HIV-1 RNA for any participant with a HIV-1 RNA ≥ 50 c/mL at Week 48 or Week 96 must be performed. The retest should be scheduled as soon as possible (but no later than 4 weeks from the Week 48 or Week 96 visits, respectively) and will inform the Week 48 or Week 96 virological endpoint, respectively.

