7.1. Time and Events Table

Note: While some assessments included in the Time and Events Table are conducted less frequently following the primary endpoint (Week 48), IM injections for participants during the Extension Phase will continue to be administered Q4W or Q8W based on original study randomization assignment.

All patients will be randomized at Day 1 to initiate either Q4 weekly or Q8 weekly administration of IM CAB LA + RPV LA. Only participants randomized from oral SOC treatment will participate in the Day 1 to Week 4 Oral CAB + Oral RPV lead-in treatment.

- h. A 12-lead ECG will be performed after resting in a semi-supine position for at least 5 minutes. ECGs will be performed pre-dose. For participants transitioning from ATLAS, the pre-dose Week 48 ECG can also serve as the ATLAS-2M Screening ECG. ECG pre-dose will be performed in triplicate at Day 1. A 2-hour post-dose ECG will also be performed at Days 1 and Week 48 for participants receiving CAB LA + RPV LA with an allowable window of ± 30 minutes.
- i. Only SAEs related to study participation or to a concomitantly administered ViiV/GSK product will be collected between obtaining informed consent and administration of study drug at Day 1.
- j. On Day 1, the eC-SSRS is to be administered prior to randomization. The eC-SSRS will preferably be completed at the beginning of the visit following administration of other PROs required prior to injections. The eC-SSRS is not required during the Withdrawal visit if withdrawal occurs during the Extension Phase.
- k. Women of childbearing potential only. SR=serum, UR=urine. Pregnancy events will be captured starting at Day 1 following initial exposure to study drug. Urine pregnancy test performed at Day 1 prior to administration of study drug, at Week 4b, and at study visits when other blood draws are not required in order to limit needle sticks. Serum pregnancy test can substitute for urine pregnancy test if locally required but must be appropriately timed to confirm pregnancy status prior to randomization and first IM administration.
- l. Week 48 and Week 96 HIV-1 RNA retest (within 4 weeks) for results > 50 c/mL will be captured as unscheduled visit. Plasma for storage samples will be used for possible future analyses.

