Columbia Suicide Severity Rating Scale (eC-SSRS) ^j	X	X		X	X		X	X	X	X		X	X	X	X	X	X	X			X	
Clinical chemistry and Hematology	X	X	X	X	X		X	X	X	X		X	X	X	X	X	X	X	X	X	X	X
Pregnancy Testing ^k	S	U	S	U	S		S	S	S	S		S	S	S	S	S	S	S	S	S	S	S
HIV-1 RNA and sample for storage (S) ^l	X	X		X	X		X	X	X	X		X	X	X	X	X	X	X	S	X	X	X
CD4+ cell count	X	X		X	X		X	X	X	X		X	X	X	X	X	X	X	X	X	X	X
CD8+ cell count		X						X				X						X			X	
Urinalysis ^m		X	X					X				X						X			X	
Fasting Labs Glucose, Cholesterol (Total, HDL and LDL) and Triglycerides ⁿ		X										X						X			X ^o	

Procedure	Screening Visit ^a		Maintenance Phase																	Extension Phase	Withdrawal Assessments ^y	Long-Term Follow-up ^z						
	Day 1	Week																										
		Week 4A (Oral lead-in ONLY) ^b	Week 4B (Oral lead-in ONLY) ^b	8	9	16	24	32	40	41	48	56	64	72	80	88	96	100	Q8W After Week 96									
Hepatitis B (HBsAg), Anti-HBc, and Anti-HBsAG, Hepatitis C (anti-HCV Ab)	X																											
PT/PTT/INR	X	X																										
PBMCs ^p		X								X								X								X		
Genetics sample ^q		X																										
PK sampling when transitioning from SOC ^r (S)=Storage only				X	X	X	X	X	X	X	X	S	S	S	S	S	X	S							X	S		
PK sampling when transitioning from CAB + RPV Q4W ^r (S)=Storage only		X			X	X	X	X	X	X	X	S	S	S	S	S	X	S							X	S		
Oral CAB and Oral RPV Dispensation ^s		X	X																									

Procedure	Screening Visit ^a		Maintenance Phase																	Extension Phase	Withdrawal Assessments ^y	Long-Term Follow-up ^z						
	Day 1	Week																										
		Week 4A (Oral lead-in ONLY) ^b	Week 4B (Oral lead-in ONLY) ^b	8	9	16	24	32	40	41	48	56	64	72	80	88	96	100	Q8W After Week 96									
IP accountability (Pill Counts)		X	X																									
IM treatment administration when transitioning from SOC ^t				X	X		X	X	X	X		X	X	X	X	X	X	X			X							
IM treatment administration when transitioning from CAB + RPV Q4W	X				X		X	X	X	X		X	X	X	X	X	X				X							
Patient Reported Outcomes ^u																												
HAT-QoL (short-form)		X						X				X															X	
HIV TSQs		X					X					X															X	
HIV TSQc ^v												X															X	
ACCEPT		X						X				X															X	

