- h. A 12-lead ECG will be performed after resting in a semi-supine position for at least 5 minutes. ECGs will be performed pre-dose. For participants transitioning from ATLAS, the pre-dose Week 48 ECG can also serve as the ATLAS-2M Screening ECG. ECG pre-dose will be performed in triplicate at Day 1. A 2-hour post-dose ECG will also be performed at Days 1 and Week 48 for participants receiving CAB LA + RPV LA with an allowable window of ± 30 minutes.
- i. Only SAEs related to study participation or to a concomitantly administered ViiV/GSK product will be collected between obtaining informed consent and administration of study drug at Day 1.
- j. On Day 1, the eC-SSRS is to be administered prior to randomization. The eC-SSRS will preferably be completed at the beginning of the visit following administration of other PROs required prior to injections. The eC-SSRS is not required during the Withdrawal visit if withdrawal occurs during the Extension Phase.
- k. Women of childbearing potential only. SR=serum, UR=urine. Pregnancy events will be captured starting at Day 1 following initial exposure to study drug. Serum pregnancy test can substitute for urine pregnancy test if locally required but must be appropriately timed to confirm pregnancy status prior to randomization and first IM administration.
- l. Week 48 and Week 96 HIV-1 RNA retest (within 4 weeks) for results > 50 c/mL will be captured as unscheduled visit. Plasma for storage samples will be used for possible future analyses.
- m. A morning specimen is preferred. To assess biomarkers: urine albumin/creatinine ratio; urine protein/creatinine ratio; and urine phosphate. Urine phosphate results from visit 4a are not required by protocol to inform the safety review at visit 4b prior to receipt of initial CAB LA + RPV LA injections.
- n. An overnight fast is preferred; however, a minimum of a 6-hour fast is acceptable.
- o. Only collect if the Withdrawal visit occurs at Week 48 or Week 96.
- p. Whole blood/PBMC collection samples may be used for virologic analyses. PBMCs will be collected at baseline Day 1, Week 48, Week 96, or Withdrawal if prior to Week 96.
- q. Genetics sample should be collected only for patients who did not participate in the 201585(ATLAS) study (sample was previously collected and stored). Informed consent for genetic research must be obtained before sample collection. Sample may be collected at any visit after signing informed consent, but preferably at the Day 1 visit.

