7.4.2. Laboratory Assessments

All protocol required laboratory assessments, as defined in the Time and Events Schedule (see Section 7.1), must be performed by the central laboratory. Laboratory assessments must be conducted in accordance with the Central Laboratory Manual and Protocol Time and Events Schedule. Laboratory requisition forms must be completed and samples must be clearly labeled with the participant number, protocol number, site/centre number, and visit date. Details for the preparation and shipment of samples will be provided by the central laboratory. Reference ranges for all safety parameters will be provided to the site by the central laboratory.

- The investigator must review the laboratory report, document this review, and record any clinically relevant changes occurring during the study in the AE section of the CRF. The laboratory reports must be filed with the source documents. Clinically significant abnormal laboratory findings are those which are not associated with the underlying disease, unless judged by the investigator to be more severe than expected for the participant's condition.
- All laboratory tests with values considered clinically significantly abnormal during participation in the study should be repeated until the values return to normal or baseline or are no longer considered significantly abnormal by the investigator or medical monitor.
- If such values do not return to normal/baseline within a period of time judged reasonable by the investigator, the etiology should be identified and the sponsor notified.
- All protocol-required laboratory assessments, must be conducted in accordance with the laboratory manual and the protocol Time and Events table.

If additional non-protocol specified laboratory assessments are performed at the institution's local laboratory and result in a change in subject management or are

considered clinically significant by the investigator (e.g., SAE or AE or dose modification) the results must be recorded in the eCRF. Local laboratory services may be used to verify pending laboratory parameters only after consultation and agreement with the study team.

Refer to the lab manual for appropriate processing and handling of samples to avoid duplicate and/or additional blood draws.

Labs will be automatically graded by the central lab according to the DAIDS toxicity scales (See Section 11.2 “Division of AIDS Table for Grading the Severity of Adult and Pediatric Adverse Events”).

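### Section 7.4.1 requires a negative urine pregnancy test before any long-acting dose, but the Q8W schedule marks serum alone at 12 of 13 injection visits through Week 96 and does not require that result before the injection

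*Protocol*

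**What the plan says.** Section 7.4.1 of the protocol makes a negative urine test a condition of dosing: "A negative urine pregnancy test is required prior to initiation of IP, any dose of CAB LA or RPV LA". Starting investigational product and any dose of the injectables are listed as separate triggers.

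The schedule is the row labelled "Pregnancy Testing ^k" in the Q8W Time and Events Table (section 7.1.2). It shows urine at Day 1 and Week 4b and serum at every injection visit from Week 8 onward.

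The other relevant provisions are:

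- **Section 7.4.2:** "All protocol required laboratory assessments, as defined in the Time and Events Schedule (see Section 7.1), must be performed by the central laboratory".
- **Appendix 7:** for pregnancy tests specifically, allows either the central laboratory or a supplied or approved kit.
- **Footnote k:** a locally required serum test used in place of urine "must be appropriately timed to confirm pregnancy status prior to randomization and first IM administration". The Q4W version adds that urine is used "at study visits when other blood draws are not required in order to limit needle sticks".
- **Section 2.3.1:** gives the purpose of testing: "FRP are also required to undergo regular pregnancy testing throughout study conduct to enable early discontinuation of CAB LA once pregnancy is identified".

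**The concern.** The dosing condition and the schedule do not match. Section 7 allows no waivers except for immediate safety concerns and makes adherence to the Time and Events Table essential, so both texts bind the site. A coordinator who works from the table draws serum at Week 8 and gives the injection at the same visit. A serum sample sent away that day is not a negative result obtained before dosing, and it is not a urine test.

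What is at stake is one avoidable dose. Intrauterine pregnancy is a mandatory reason to stop treatment (section 5.5). An injected dose cannot be withdrawn, and section 6.9.1 notes that both drugs may remain measurable in plasma for more than a year. There is also a conduct cost: sites may act differently, and a monitor could cite a deviation under either reading.

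**Working it through.** The plan states no figure on this point, so the check is a count of scheduled visits followed by a reading of the timing rules.

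**Injection visits, from the dosing text.** Section 4.2.2 is used because the injection rows of the extracted table are partly misaligned.

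- Entry from oral standard of care: Week 4b, Week 8, then "Week 16 visit and Q8W thereafter - CAB LA 600 mg + RPV LA 900 mg IM, every 8 weeks for 100 weeks". Visits through Week 96 are 4b, 8, 16, 24, 32, 40, 48, 56, 64, 72, 80, 88 and 96. Count: 1 + 12 = 13.
- Entry from ATLAS Q4W: Day 1, then "Week 8 and Q8W thereafter- CAB LA 600 mg + RPV LA 900 mg IM". Visits are Day 1 and Weeks 8 to 96 in steps of 8. Count: 1 + 12 = 13.

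**Specimen at each visit, from the Q8W pregnancy row.** The row has 22 cells for 22 columns. Its two blanks fall on Weeks 9 and 41, the one-week post-dose PK visits at which no injection is given, so the alignment holds.

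| Column | Mark |
|---|---|
| Screening | S |
| Day 1 | U |
| Week 4a | S |
| Week 4b | U |
| Week 8 | S |
| Week 9 | blank |
| Weeks 16, 24, 32, 40 | S |
| Week 41 | blank |
| Weeks 48 to 96, every 8 weeks | S |
| Week 100, Extension, Withdrawal, long-term follow-up | S |

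The cells read S and U, while footnote k defines SR as serum and UR as urine. Reading S as serum and U as urine is the natural interpretation.

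**Count.** From standard of care, urine falls on Week 4b only; from ATLAS, on Day 1 only. Serum alone is therefore marked at 12/13 = 92% of injection visits through Week 96 on either route, and at 6/7 = 86% through Week 48.

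**Does any text require the serum result before those 12 injections?**

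- The serum-availability sentence in 7.4.1 covers locally required serum at visits where urine is already the indicated test, which excludes Week 8 onward.
- Footnote k stops at randomization and the first injection.
- Section 7.4.2 and Appendix 7 say where the test is run, not when the result is needed.
- Section 7.4.7.1 and note h to Table 8 refer back to the Time and Events Table.
- By contrast, section 4.2.2.1 does hold the first injection until the Week 4a central laboratory results have been reviewed. Later doses have no equivalent.

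**Scale.** Section 9.1 gives about 510 participants per arm, and section 1.3.2 sets a goal of about 25% women: 510 × 0.25 = 127.5 women on Q8W. The share of childbearing potential is not given, so 50% to 100% is assumed, with no attrition.

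- At 100%: 127.5 × 12 = 1,530 serum-only injection visits through Week 96.
- At 50%: 63.75 × 12 = 765.

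These are visits without a scheduled urine test. They are not visits shown to lack a pre-dose result, and they are not pregnancies.

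**The case against.** The strongest reply is that the safeguard is already written. Read literally, 7.4.1 demands a pre-dose negative before any injection, and a site can run a urine kit beside the scheduled serum draw, so the two provisions can both be met. This stands, and it limits the defect to a table that fails to mark a test the text requires.

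The alternative reply is that only a first-dose gate was meant. The 7.4.1 list is introduced as following the schedule, section 7.4.7.1 and note h to Table 8 defer to it, and footnote k ties confirmation to randomization and the first injection. The Q4W footnote suggests that serum at blood-draw visits was chosen to spare needle sticks. This is plausible, but it explains the choice of specimen and leaves the any-dose wording of 7.4.1 too broad. On either reading one of the two texts needs correcting.

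A reader might infer that women on Q8W are injected without pregnancy testing. The schedule refutes that: a test is marked at every Q8W injection visit. A reader might also infer that the serum result must come from the central laboratory and so could never be ready in time. Appendix 7 permits a kit, so this cannot be said. Nor does section 2.3.1 promise a result before each dose; it promises regular testing so that treatment can be stopped early, which the serum samples provide.

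The safety margin also counts in the plan's favour. Highly effective contraception is required from 30 days before the first dose until at least 52 weeks after the injectables are stopped. Testing on a missed cycle or on suspicion is required. The reduced rat-pup survival in section 2.3.1 occurred at the maximum tested dose, and maternal exposure at the no-effect dose was more than 20-fold the predicted clinical exposure.

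**Conclusion.** The mismatch is real and minor. Section 7.4.1 sets a urine precondition for every long-acting dose. The Q8W table supports it at 1 of 13 injection visits through Week 96, and no rule requires the serum result first at the other 12.

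The avoidable harm is at most one further dose of CAB LA 600 mg plus RPV LA 900 mg per unsuspected pregnancy found by a scheduled test, assuming the serum result returns before the next visit 8 weeks later. A pre-dose test at Week 8 or later cannot prevent exposure altogether, because on-schedule participants have by then already received long-acting drug.

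It would be tempting to extend the count to the Q4W arm. The body of that table is not in the available text, and its footnote schedules urine at visits without other blood draws, so no Q4W claim is supported. Confidence is medium because of that absence and the difference between the S/U cells and the SR/UR codes.

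**What to change.** In the Q8W pregnancy row, mark a pre-dose urine kit test at each injection visit for women of childbearing potential and keep the existing serum samples. Keep the local-serum provisions in 7.4.1 and footnote k tied to randomization and the first injection; otherwise the 7.4.1 sentence would reach the newly marked visits and could call for extra early draws.

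The cost is one table row and one urine kit per injection visit. That is about 765 to 1,530 additional kits through Week 96 under the assumptions above, with no added blood draw. The Extension Phase column is also marked serum and would follow the same rule; its kits are not counted because its length varies by country.

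If the sponsor intends only a first-dose gate, narrow the 7.4.1 sentence to the start of investigational product and the first injection, with later testing per the Time and Events Table. That costs one sentence and no kits.

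For Q4W, check the table for the same mismatch and change nothing else.
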